11.3.3.1 Response to QTc(F) Interval Prolongation

The following guidelines should be used in the management of QTc(F) prolongation. Subjects will have ECGs performed at times designated by the protocol (ECGs will be repeated 3 times consecutively within 30 minutes [must have an interval of at least 1–2 minutes between ECGs]). If the average QTc(F) interval increases to > 60 msec above the highest average predose value (average of Day 1 predose and screening values) or to the level of ≥ 480 msec according to local site analysis:

• Hold study drug until central read is confirmed.

- Check electrolytes, especially magnesium and potassium; correct abnormalities as clinically indicated.
- Obtain blood sample for PK analysis.
- Manage as clinically indicated with cardiology consultation as needed.
- Contact medical monitor to discuss additional monitoring.

If results are confirmed by the central reader, the subject may be removed from the study after discussion with the medical monitor. If the subject continues in the study, discuss with the medical monitor appropriate management (including possibility of dose reduction) and ECG follow-up.

11.3.4 Elevated Amylase

If subjects develop an elevated serum amylase during the study that is >1.5 ×ULN, then additional evaluations should be performed. These should include evaluating serum lipase, amylase isoenzymes, and fasting triglycerides as well as obtaining history regarding symptoms of pancreatitis, symptoms of dry mouth, and use of alcohol. The subject should have a drug holiday for 28 days, with amylase measured at the end of the drug holiday. If the amylase is within normal range after the end of the drug holiday, tesevatinib may be restarted at a reduced dose, and amylase measured approximately 14 days later, and then at the start of each cycle of tesevatinib administration. If results continue to be abnormal, the subject will be removed from study. If an elevated serum amylase that is >1.5 ×ULN occurs a second time, the subject will be removed from the study.

11.3.5 Elevated Creatinine Phosphokinase

If subjects develop an elevated serum CPK during the study that is >2.0 ×ULN, additional evaluations should be performed. These should include evaluating serum CPK isoenzymes as well as obtaining history regarding muscle-related symptoms or strenuous or prolonged exercise.

11.3.6 Pulmonary Toxicity

If subjects experience an acute onset of new and/or progressive, unexplained pulmonary symptoms such as dyspnea, cough, and fever, study drug should be held while subjects are

evaluated. If interstitial lung disease (ILD) is diagnosed, study drug should be discontinued and treatment administered as necessary.

11.3.7 Hepatotoxicity

Rare cases of hepatic failure have been reported. Confounding factors have included pre-existing liver disease or concomitant hepatotoxic medications. Liver function test abnormalities (including elevated ALT, AST, and bilirubin) have been observed in clinical studies with tesevatinib. Interruption of study drug should be considered in subjects developing liver function abnormality $\geq 3x$ ULN

Dose Modifications for Hyperbilirubinemia

	> ULN 2.5 × ULN	2.5– <3 × ULN	>3 × ULN	
KD019	Treat at same dose level	1 st Occurrence: Hold dose; reduce 1 dose	1 st Occurrence: Off Study	
	ievei	level when recovered to	On Study	
		mild intensity.		
		2 nd Occurrence:		
		Off study		

Dose Modifications for Transaminitis (AST/ALT)

	> ULN – 2.5 × ULN	2.5– <3 × ULN	>3 × ULN	
KD019	Treat at same dose level	1 st Occurrence: Hold dose; reduce 1 dose level when recovered or reduced to mild intensity.	1 st Occurrence: Hold dose and discuss management with Medical Monitor	
		2 nd Occurrence: Hold dose and discuss management with Medical Monitor	2 nd Occurrence: Off study	

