Appendix C: Clinical Symptom and Adverse Event Grading Scale

CLINICAL ADVERSE EVENT GRADING SCALE			
Severity	Grade	Definition	
Mild	1	Awareness of symptom, but easily tolerated. Usually transient requiring no special treatment; does not interfere with usual status or activities	
Moderate	2	May be ameliorated by simple therapeutic measures; may interfere with usual activities	
Severe	3	Incapacitating; unable to perform usual activities	
Life-threatening	4	Requires immediate intervention; need for emergency treatment	
Death	5	Resulting in the subsequent death of the subject	

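### Protocol Section 11.3.7 gives inconsistent instructions for the same liver values: its text makes interruption optional from 3 × ULN, while its tables require a hold or withdrawal above 3 × ULN and start action at 2.5 × ULN

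*Protocol*

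**What the plan says.** Section 11.3.7 of the protocol has three parts.

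- **The sentence.** After reporting that ALT, AST and bilirubin abnormalities have been seen with tesevatinib, it says "Interruption of study drug should be considered in subjects developing liver function abnormality", with a threshold of 3 × ULN or more.
- **The bilirubin table.** Same dose up to 2.5 × ULN. From 2.5 to below 3 × ULN, the first-occurrence entry begins "1 st Occurrence: Hold dose; reduce 1 dose" (one level, after recovery to mild intensity), and a second occurrence is off study. Above 3 × ULN the entry is "1 st Occurrence: Off Study".
- **The AST/ALT table.** Same dose up to 2.5 × ULN. From 2.5 to below 3 × ULN, "1 st Occurrence: Hold dose; reduce 1 dose level when recovered or reduced to mild intensity"; a second occurrence means hold and discuss. Above 3 × ULN, "1 st Occurrence: Hold dose and discuss management with Medical Monitor", and a second occurrence is off study.

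Elsewhere, Section 11.3 lets the investigator hold drug for up to 28 days unless a later subsection specifies otherwise. Section 10.1 lists general reasons for withdrawal and contains no liver rule. Sections 13.1 and 13.3.6 grade toxicities and adverse events by Appendix C, where mild begins "Awareness of symptom, but easily tolerated". Section 13.3.8 grades clinically significant laboratory abnormalities by CTCAE.

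**The concern.** A dose-modification rule should give one instruction for one laboratory value. Here the sentence and the tables cover the same analytes, but they differ in force above 3 × ULN and in the level at which action starts. The difference is largest for bilirubin above 3 × ULN: one line leaves continued dosing open and the other ends participation.

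Two things are at stake. The first is subject safety and uniform conduct, because Section 11.3 lists hepatotoxicity among the adverse events associated with tesevatinib. The second is the data. A subject taken off study before Day 28 does not meet the 28-day completion condition for the mITT population (SAP Section 3.2), which is used for the primary GFR analysis (SAP Section 3.7). A subject withdrawn later contributes no 6-month value. The SAP tables of TEAEs leading to dose modification and discontinuation (14.4.10 to 14.4.13) would also partly reflect which line each site followed.

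**Working it through.** No sample size, power or event figure is involved, so there is no plan figure to reproduce. The check sets the sentence against the two tables, band by band, as printed.

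| Value (× ULN) | Sentence | Bilirubin table, 1st occurrence | AST/ALT table, 1st occurrence | Relation |
|---|---|---|---|---|
| Above 1, below 2.5 | silent | same dose | same dose | no conflict |
| Exactly 2.5 | silent | see note | same dose and hold both apply | AST/ALT bands overlap |
| Above 2.5, below 3 | silent | hold, then reduce one level | hold, then reduce one level | different starting level |
| Exactly 3.0 | consider interruption | no column | no column | only the optional rule applies |
| Above 3 | consider interruption | off study | hold and discuss | direct conflict in force |

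Note: the first bilirubin column header has lost its dash in the text available, so the overlap at 2.5 is claimed for AST/ALT only.

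Worked values:

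1. Bilirubin 3.2 × ULN. Since 3.2 ≥ 3, the sentence applies and interruption is optional. Since 3.2 > 3, the table applies and the subject is off study.
2. ALT 3.2 × ULN. The sentence makes interruption optional; the table requires a hold and a discussion with the medical monitor.
3. ALT 2.7 × ULN. Since 2.7 < 3, the sentence is not triggered. Since 2.5 ≤ 2.7 < 3, the table requires a hold. The two lines differ on where action starts, but the sentence does not tell the site to continue.
4. Exactly 3.0 × ULN. The columns end below 3 and resume above 3, so no table entry applies. Read literally, 2.9 requires a hold, 3.0 only consideration, and 3.1 again a hold (AST/ALT) or withdrawal (bilirubin).

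Is precedence settled elsewhere? The proviso in Section 11.3 makes Section 11.3.7 override the general holding discretion, but it does not rank the sentence within 11.3.7 against the tables within 11.3.7. Section 10.1 does not address liver values. The sentence cannot easily be confined to other liver tests, because the sentence before it names the same three analytes as the tables.

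Is recovery to mild intensity defined? Section 13.1 points to Appendix C, which is symptom-based. Section 13.3.8 points to CTCAE for clinically significant laboratory abnormalities. Section 11.3.7 cites neither, so the restart condition depends on which scale a site applies.

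How close can subjects start? Inclusion criterion 6 admits AST and ALT below 2.5 × ULN, so a subject may enter just under the level at which the tables begin to act. Liver tests in the SILK cohort are drawn on Days 7, 14, 21 and 28 (Table 4-1), so the rule can come into play before Day 28.

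**The case against.** The strongest reply is that the tables are the more specific instruction and a sensible site would follow them, treating the sentence as background. That is a reasonable inference, but the protocol does not say it, and a participation-ending rule should not rest on inference.

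Other objections stand and limit the point:

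- A reader might infer that the sentence and tables contradict each other in every band. They do not. From 2.5 to below 3 × ULN the sentence is silent, so only the table speaks; the difference there is in the starting level.
- A reader might infer from Appendix C that an asymptomatic rise is already mild when drug is held, so that the recovery condition is empty. That ignores Section 13.3.8. What remains is that Section 11.3.7 does not name the scale.
- A reader might count every SILK and continuing subject as affected. They are covered by the rule, but the documents do not say how many reach 2.5 × ULN. The adverse events of special interest listed for this study in Section 5.3.1 include no liver event, and the remark on hepatic failure in Section 11.3.7 does not itself attribute those cases to tesevatinib.
- The 2.5 and 3.0 × ULN points concern single exact values, and a lost inequality sign cannot be excluded, although both tables show the same strict sign above 3. A stray fragment in the bilirubin column that seems to say the opposite of off study looks like a text-reading error and is not relied on.
- The affected SAP tables are descriptive, in an open-label, nonrandomized study, and no GFR formula depends on this section. The effect on the data runs only through who stays on drug and on study.

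**Conclusion.** The inconsistency is real and lies within one section. Above 3 × ULN, the same value carries an optional action in the text and a required one in the tables: withdrawal at first occurrence for bilirubin, and hold and discuss, then withdrawal at second occurrence, for AST/ALT. The tables also begin to act 0.5 × ULN lower than the sentence (3 − 2.5). Nothing in Sections 11.3 or 10.1 ranks one over the other. The band edges and the undefined recovery scale are minor additions.

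The size in subjects cannot be given, because neither document reports an incidence of liver values at these levels. The rule covers up to 50 SILK subjects and those still on treatment, which is an upper limit on exposure to the rule and not an estimate of effect. The conclusion assumes that the thresholds and the off-study entry are as printed. The documents do not support saying that the two parts conflict at every level, or that the restart condition is void.

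**What to change.** The sponsor should:

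1. Reconcile the sentence in Section 11.3.7 with the two tables, or state which of them governs.
2. Make the table bands contiguous, so that each value, including exactly 2.5 and 3.0 × ULN, falls in one column.
3. State which grading scale the recovery term (mild intensity) refers to: Appendix C or CTCAE, and if CTCAE, which version.

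The thresholds, the actions and the tiering by band and occurrence are clinical decisions for the sponsor; this point asks only that the passages agree. The cost is a few lines of wording in a protocol amendment, with no new tests or visits.

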11.3.8 Pericardial Effusion

Pericardial effusions have been seen in oncology studies with tesevatinib. In addition, 1 subject with ADPKD receiving 50 mg tesevatinib daily developed a trace pericardial effusion. The

following guidelines should be followed in the event that a subject develops a pericardial effusion while receiving tesevatinib:

For an asymptomatic pericardial effusion that is at least moderate in size, a follow-up echocardiogram should be performed within 1–3 months to monitor for progression. Discuss results of the additional echocardiogram with the medical monitor to determine subject management.

Subjects should be monitored for signs and symptoms of cardiac tamponade. In addition to the monthly to bimonthly physical exam of blood pressure, pulse, respiration, weight, heart, and lung, physical exam should also asses for tachycardia, dyspnea, neck vein distension, and edema.

11.3.9 Adrenal Insufficiency

One case of adrenal insufficiency has been reported in an oncology subject receiving tesevatinib. Subjects should be monitored for signs or symptoms of adrenal insufficiency and the medical monitor immediately notified if symptoms are observed.

11.4 Study Drug Accountability and Subject Treatment Compliance

Drug accountability and subject treatment compliance will be assessed using drug dispensing and return records. The principal investigator is responsible for ensuring adequate accountability of all used and unused study drug. While the principal investigator may delegate components of drug accountability tasks to documented designee(s) (eg, pharmacist), the ultimate responsibility for drug control and accountability resides with the investigator. This includes acknowledgment of receipt of each shipment of study drug (quantity and condition) and the maintenance of subject dispensing records and returned study product documentation. Dispensing records will document quantities received from Kadmon and quantities dispensed to subjects, including lot number, date dispensed, subject identification number, subject initials, and the initials of the person dispensing study drug. Reasons for deviation from the expected dispensing regimen also must be recorded.

At study initiation, the study monitor will evaluate and obtain a copy of each site's written standard operating procedure for study drug disposal/destruction in order to ensure that it complies with the requirements of Kadmon.

At the end of the study, following final drug inventory reconciliation by the monitor, the study site will dispose of and/or destroy any remaining unused study drug supplies, including empty containers, according to institutional procedures for destruction, reviewed and approved by Kadmon prior to material destruction. If the site cannot meet the requirements of Kadmon for disposal, arrangements will be made between the site and Kadmon or its representative, for destruction or return of unused study drug supplies.

All drug supplies and associated documentation will be periodically reviewed and verified by the study monitor over the course of the study.

12 CONCOMITANT MEDICATION AND TREATMENT

If the subject must use a concomitant medication during the study, it is the responsibility of the principal investigator to ensure that details regarding the medication are recorded on the eCRF.

Subjects should avoid ingesting grapefruit, pomelo or Seville fruit (and juice) with tesevatinib or at any time during the study. Subjects should not take medications that are associated with a risk of QTc(F) interval prolongation and/or torsades de pointes. Additionally, subjects are not permitted to take concomitant medications that inhibit (eg, ketoconazole, itraconazole, erythromycin, clarithromycin) or induce (eg, dexamethasone, phenytoin, carbamazepine, rifampicin, or phenobarbital) the CYP3A4 isozyme. Tesevatinib is also highly protein bound, and other drugs that are also highly protein bound with the exception of warfarin (eg, diazepam, furosemide, dicloxacillin, propranolol, and phenytoin) should be avoided.

Antiemetics and antidiarrheal medications should not be administered prophylactically before initial treatment with study drug. At the discretion of the investigator, treatment of symptoms with antiemetic and antidiarrheal medications may be undertaken per standard clinical practice.

Since tesevatinib is a potent inhibitor of MATE transporter proteins, increased levels of concomitant medications that are secreted by the kidney proximal tubule cells into the renal tubule by MATE transporter proteins may occur. Thus, subjects taking cephalexin, cimetidine, dofetilide, fexofenadine, metformin, procainamide, and pyrimethamine should be monitored carefully.

12.1 Additional Therapy

A subject should not receive additional therapeutic treatment during the study period without the approval of the sponsor's medical monitor.

12.2 Interaction of Tesevatinib with Other Medications

12.2.1 Tesevatinib

Microsomal oxidation of tesevatinib involves CYP3A4; the percentage conversion of tesevatinib in human microsomes was low. This suggests a low potential for other drugs to significantly affect the biotransformation of tesevatinib in humans through interaction with CYP-mediated metabolic pathways.

P-glycoprotein (P-gp) is extensively expressed in multiple tissues and is involved in the transport of a vast variety of biological molecules. It is not possible to screen for all drugs possibly influenced by p-glycoprotein but will monitor the main drugs such as colchicine, verapamil, tamoxifen, cyclosporine, and digoxin.

12.2.2 Management of Subjects Requiring Concomitant Medications Associated with QT Interval Prolongation

Tesevatinib has been associated with prolongation of the QT interval. Subjects requiring treatment with drugs known to be associated with torsades de pointes or significant QT interval prolongation may not be enrolled into this study. This includes Class IA antiarrhythmics (eg, quinidine, procainamide); Class III antiarrhythmics (eg, amiodarone, sotalol, dofetilide); phenothiazine anti-psychotics: (eg, chlorpromazine, mesoridazine, pimozide, thioridazine); quinolone antibiotics: (eg, gatifloxacin, moxifloxacin, sparfloxacin); macrolide antibiotics (eg, erythromycin, clarithromycin, and troleandomycin) and other drugs that have a contraindication or boxed warning regarding QT prolongation in the prescribing information.

Appendix B, Concomitant Medications Associated with a Risk of QTc(F) Interval Prolongation and/or Torsades de Pointes, contains a partial list of drugs associated with a risk of QT interval prolongation and/or torsades de pointes.

Drugs associated with QT interval prolongation should be avoided in subjects receiving study drug. Should a subject develop a condition for which a medication known to affect QT interval is indicated, consideration should be given to the additive risk of QT interval prolongation versus the potential benefit of treatment with the required medication and/or study drug. Contact the medical monitor prior to the administration of the concomitant medication.

During the follow-up period, subjects who require short-term (2 to 3 weeks, not to exceed 21 days) treatment with a concomitant medication associated with QT interval prolongation should have the study drug held until the concomitant treatment course is complete. The decision about whether the subject can continue on study following this interruption will be determined by the medical monitor. If the subject restarts study drug after discussion with the medical monitor, an ECG will be performed prior to restarting study drug.

13 SAFETY

13.1 Safety Parameters

The 5-point Clinical Symptom and Adverse Event Grading Scale will be used for grading toxicities (see Appendix C). Subjects will be monitored throughout the treatment and follow-up period for occurrence of AEs (acute, delayed, and/or cumulative), as well as for changes in clinical status, vital sign measurements, and laboratory data. Safety parameters to be measured/assessed include eligibility assessment, medical history, vital sign measurements, physical examinations, concomitant medications, hematology, serum chemistries, coagulation profiles, peripheral blood smears, renal function (creatinine clearance and cystatin C), urinalysis, pregnancy testing, ECGs, and echocardiograms.

13.2 Adverse Event Definition

An adverse event (AE) is defined as any unintended or undesirable, noxious, or pathological change, compared to pre-existing conditions, experienced by a subject during a clinical study or the follow-up period, regardless of relationship to study drug. Adverse events include:

- Suspected adverse drug reactions
- Reactions from drug overdose, abuse, withdrawal, sensitivity, or toxicity
- Significant changes or abnormalities, when compared to baseline, in structure (sign), function (symptom), clinical laboratory results, ECG results, or physiological testing. This includes any worsening of a pre-existing condition temporally associated with the use of study drug
- Pre- or post-treatment complications that occur as a result of protocol-mandated procedures
- Pre-existing events, that increase in intensity/severity or change in nature
- Other medical events, regardless of their relationship to the study drug, such as injury, surgery, accidents, extensions of symptoms, or apparently unrelated illnesses

For the purpose of data collection, all untoward events that occur after informed consent through 30 days after the last dose of tesevatinib must be recorded on eCRFs by the investigational site. This requirement includes AEs from unscheduled as well as scheduled visits.

An AE does not include:

- Medical or surgical procedures (eg, surgery, endoscopy, tooth extraction, transfusion); when the condition that leads to the procedure is an adverse event.
- Pre-existing diseases, or conditions or laboratory abnormalities present or detected prior to the screening visit, those do not worsen.
- Situations where an untoward medical occurrence has not occurred (eg, hospitalization for elective surgery, social, and/or convenience admissions).
- Overdose of either KD019 or a concomitant medication without any signs or symptoms, unless the subject is hospitalized for observation.

13.3 Evaluating Adverse Events

The investigator will determine the seriousness, intensity (severity), and causality (relationship) of an AE associated with the use of the study drug (ie, events where there is a reasonable possibility that the event may have been caused by the study drug) based on the following definitions:

13.3.1 Serious Adverse Events

(Notify sponsor or designee within 24 hours of first awareness; document on eCRF)

The SAE definition and reporting requirements are in accordance with the ICH Guideline for Clinical Safety Data Management, Definitions, and Standards for Expedited Reporting, Topic E2A.

An SAE is any untoward medical occurrence that at any dose results in any of the following outcomes, regardless of relationship to study drug:

• Death: Any death that occurs while the subject is "on study" as well as any death that occurs within 30 days after the last dose of study drug.

Note: Death is an outcome of an AE, and not an AE in itself. The event(s) that caused death (eg, illness, accident) constitutes the SAE.

• Life threatening: Any adverse drug event that places the subject, in the view of the investigator, at immediate risk of death from the reaction as it occurred (ie, this does not include a reaction that had it occurred in a more severe form, might have caused death).

• Inpatient hospitalization or prolongation of existing hospitalization: any AE requiring in-patient hospitalization. A visit to the emergency room or hospital clinic would not be considered in-patient hospitalization; however, it could be considered serious if medical intervention was necessary in order to prevent a serious outcome.

"In-patient hospitalization" means the subject has been formally admitted to a hospital for medical reasons, for any length of time. This may or may not be overnight. It does not include presentation to and care within an emergency department.

In the absence of an AE, the investigator should not report hospitalization or prolongation of hospitalization. Examples are the following:

- Hospitalization or prolongation of hospitalization is needed for a procedure required by the protocol.
- Hospitalization or prolongation of hospitalization is part of routine procedure followed by study center.
- o Hospitalization for survey visits or annual physicals.

In addition, a hospitalization planned before the start of the study for a pre-existing condition which has not worsened would not be considered an SAE. Complications that occur during hospitalizations are AEs. If a complication prolongs hospitalization, it is an SAE.

- Persistent or significant disability/ incapacity: Any substantial disruption of a person's ability to conduct normal life functions.
- Congenital anomaly/birth defect
- Important medical event: Any adverse event that may not result in death, that may not be immediately life threatening, or require hospitalization may be considered a SAE when, based upon appropriate medical judgment, it may jeopardize the subject and may require medical or surgical intervention to prevent an SAE outcome.

